Number of subjects was based on a power analysis using FVC/FEV₁ as the primary variable and stratified by unilateral versus bilateral diagnosis. Previous literature suggests a standard deviation of approximately 0.20-0.60 for FVC/FEV₁ values. SD was set at 0.40. Unilateral control was estimated to be 50% of predicted values (FVC/FEV₁) due to the nature of the injury, set at approximately 1.50L, with bilateral set at approximately 1.35L. Unilateral experimental group means were increased by 20% of predicted values to 1.80L, and bilateral to 1.50L. The required sample size to achieve 80% power to detect difference between splint and control groups is 104, with each group requiring 26 subjects each. Power calculations were performed in R version 4.0.0 with the pwr2ppl package, using the anova2x2 function.

Number of subjects to be used are 150 to account for withdrawals, incomplete data sets, extraneous results, etc. This is a single site study.

7) Recruitment Methods

Respiratory Therapy is part of the trauma multi-disciplinary team. and is involved with the care of every trauma patient admitted to Penrose Hospital. During trauma rounds in the ICU and floor patients that met criteria for the study will be identified. The investigators will approach those identified patients for potential enrollment in the study. Note they will not approach any patient for consent that is under their care that shift. There are no flyers or advertisements for this research or device.

8) Study Timelines

It is estimated that it will take at least one year to complete this study to include enrollment, subject completion, and all analysis. All primary variables and analyses should be completed by this time.

9) Study Endpoints

The primary endpoint of this study is to investigate the use of the Duracore splinting device in patients with chest trauma. Hospital length of stays, time to ambulation, a patient satisfaction survey, incentive spirometry, forced vital capacity measurements, and the injury severity score will be correlated to a control group to determine its' effectiveness. The quantitative data points will be collected over the first three days of hospital stay and 24 hours prior to discharge. The qualitative data will be collected prior to patient discharge. The hypothesis of this study is that the use of the Duracore splinting device will reduce hospital length of stays and improve patient lung capacities over the course of admission following chest trauma.

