The design of this study is a randomized experimental trial. The procedures involved in this study will first include obtaining the individual's consent to participate. Incentive spirometry is a standard of care that has been proven to improve deep breathing for patients. FVC/FEV₁ measurements are not always routinely done at this site but has been proven to be an indicator in respiratory deterioration in this population. Enrollment of each subject will be on a one to one basis for control and experimental groups. The trial will be randomized to reduce bias by randomly selecting patients between control and experimental groups by alternating every other patient receiving the treatment. Height, sex, ethnicity, and age will be accounted for as well to calculate the percent predicted FVC/FEV_1 to reduce statistical error. Enrollment will be based on patient consent. After enrollment into the study after admission to the hospital, baseline values of incentive spirometry (IS) and spirometry will be done. The patient will then be placed in the experimental or control group after being assigned a group via envelope randomization. If the patient is under experimental, they will receive a splinting device for treatment. Control groups will receive standard of care treatment without the splinting device. Continued analysis of IS and FVC/FEV₁ will occur over three days, and a final collection prior to discharge. Discharge planning will be coordinated with respiratory therapy, so the patient does not go home without completing the survey and final analysis. The patient satisfaction survey will be a paper survey administered to the patient. Patient identifying information will not be present on this form to maintain confidentiality. The patient will be asked if they would like to complete the form and that it is an anonymous short survey to help with identifying how the patient felt about the research. The subject will only be enrolled in the study for the duration of their hospital stay as an inpatient. There will be no follow-up after discharge, and any patients who are discharged without completing the final analysis will be omitted from the study.

11) Data Analysis Plan

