Data analysis will include a two-tailed t-test to account for significance between control and experimental groups. This will be done with both incentive spirometry and FVC/FEV₁. Correlations will be made with time to ambulation and length of stays, as well as injury severity score. Graphic representation of trends will also be used to demonstrate differences between the groups. Qualitative analysis will include providing averages from the questionnaire using a Likert scale. These averages will be used to determine whether the population felt the device provided any help with their chest trauma. Number of subjects was based on a power analysis

using FVC/FEV₁ as the primary variable. Previous literature suggests a standard deviation of approximately 0.20-0.60 for FVC/FEV₁ values. SD was set at 0.40. Unilateral control was estimated to be 50% of predicted values (FVC/FEV₁) due to the nature of the injury, set at approximately 1.50L, with bilateral set at approximately 1.35L. Unilateral experimental group means were increased by 20% of predicted values to 1.80L, and bilateral to 1.50L. The required sample size to achieve 80% power to detect difference between splint and control groups is 104, with each group requiring 26 subjects each. Power calculations were performed in R version 4.0.0 with the pwr2ppl package, using the anova2x2 function. Number of subjects to be used are 150 to account for withdrawals, incomplete data sets, extraneous results, etc. This is a single site study.

Patient satisfaction surveys will use a numbered Likert Scale. The averages of each answer will be used to reinforce the efficacy of the device and correlate to primary data. Randomization will occur by experimenter-blinded envelope randomization.

12) Provisions to Monitor the Data to Ensure the Safety of Subjects

Subjects will be monitored for the duration of their stay by all staff members, and any adverse events related to the device itself will be reported accordingly. This device claims minimal risk to patients due to its unrestrictive and non-invasive nature but will be monitored by investigators for any adverse effects. **The Data Safety Monitoring staff will review all documentation accordingly at least quarterly.**

13) Withdrawal of Subjects

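### The trial is sized with a 2x2 ANOVA but analysed with a plain t-test that leaves out fracture side and the pre-assignment baseline, so power is given away for nothing

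*Combined protocol and SAP*

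**What the plan says.** Sections 6 (Number of Subjects) and 11 (Data Analysis Plan) give the same sample-size argument. There are four groups of 26, formed by splint or control crossed with unilateral or bilateral fracture. Control means are "set at approximately 1.50L, with bilateral set at approximately 1.35L", the experimental means are "increased by 20% of predicted values to 1.80L, and bilateral to 1.50L", and "SD was set at 0.40". The result is that "The required sample size to achieve 80% power to detect difference between splint and control groups is 104", and on method, "Power calculations were performed in R version 4.0.0 with the pwr2ppl package, using the anova2x2 function". Enrolment is set at 150 to cover losses.

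The only between-arm test in section 11 is this: "Data analysis will include a two-tailed t-test to account for significance between control and experimental groups". On outcomes it adds: "This will be done with both incentive spirometry and FVC/FEV₁". It mentions no ANOVA, stratum term, baseline covariate or change from baseline, and no time point for the test.

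Section 3 (Objectives and Hypothesis(es)) describes the groups as stratified by fracture side. Section 10 (Procedures Involved) states that after enrolment "baseline values of incentive spirometry (IS) and spirometry will be done", and places group assignment after that step.

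**The concern.** A power figure belongs to a particular test. The 104 assumes that fracture side is in the model, so that the 0.40 is the spread within each of the four groups. A two-arm t-test pools the fracture types, and the difference between them becomes noise. The stated 80% therefore does not describe the planned test.

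The baseline matters more. Each patient has the same measurement taken before assignment, which is normally a strong predictor of later values. If it is left out, two costs follow: the standard error is larger than it need be, and any chance difference between arms in starting lung function stays in the treatment estimate.

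The four groups of 26 may also lead the analyst to run the t-test separately within each fracture type. The 80% does not apply there, and a non-significant bilateral result would say little.

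**Working it through.** **Inputs** (sections 6 and 11): unilateral means 1.50 and 1.80 L, bilateral means 1.35 and 1.50 L, within-group SD 0.40, 26 per group. **Assumed:** two-sided alpha 0.05, equal groups, and a within-group baseline-to-follow-up correlation r, for which the documents give no value.

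**1. Reproduce the 104.**
- The splint effects are 0.30 L (unilateral) and 0.15 L (bilateral), with mean (0.30 + 0.15)/2 = 0.225 L.
- For the ANOVA main effect, the noncentrality is λ = N × (0.225/2)² / 0.40², with 1 and N − 4 degrees of freedom.
- At 25 per group (N = 100), λ = 7.91 and power is 79.5%.
- At 26 per group (N = 104), λ = 8.23 and power is 81.1%.

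So 26 is the smallest group size that reaches 80%. The stated figure reproduces, with fracture side in the model.

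**2. Planned t-test at N = 104.**
- Pooling fracture types adds half the unilateral–bilateral gap, squared, to each arm's variance. The gap is 0.15 L in control (half is 0.075) and 0.30 L in experimental (half is 0.15).
- SD = √(0.16 + (0.075² + 0.15²)/2) = 0.417.
- Standard error = 0.417 × √(2/52) = 0.082 L, and the noncentrality is 0.225/0.082 = 2.75.
- Power is 77.8%. Simulation with exactly 26 per group gives about 78.5%.
- The t-test reaches 80% at N = 110.

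**3. Add the baseline to fracture side.** The residual SD becomes 0.40 × √(1 − r²), with 99 error degrees of freedom.

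| Analysis at N = 104 | Residual SD | Standard error (L) | Power |
|---|---|---|---|
| Unadjusted t-test | 0.417 | 0.082 | 77.8% |
| 2x2 ANOVA | 0.400 | 0.078 | 81.1% |
| With baseline, r = 0.3 | 0.382 | 0.075 | 84.6% |
| With baseline, r = 0.5 | 0.346 | 0.068 | 90.7% |
| With baseline, r = 0.7 | 0.286 | 0.056 | 97.8% |

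At r = 0.1 and 0.2 power is 81.5% and 82.6%, little more than the ANOVA.

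**4. Within fracture type, 26 v 26.** The standard error is 0.40 × √(2/26) = 0.111 L. Power is 75.6% for the unilateral effect (0.30 L) and 26.4% for the bilateral effect (0.15 L). Power for the interaction is 15.7%.

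**5. Chance baseline imbalance.** If the baseline SD is also 0.40 (assumption), the difference in arm means at baseline has standard error 0.40 × √(2/52) = 0.078 L. The chance of a difference above 0.08 L in either direction, more than a third of the 0.225 L target, is about 31%.

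**The case against.** The strongest reply is that the loss shown from the protocol's own figures is small: about 3 points, leaving power some 1.5 to 2 points under 80%. The t-test also remains valid. With balanced groups it is slightly conservative, with simulated type I error of 4.3%. This stands, and it is why the point concerns efficiency and not bias.

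Second, 150 patients are to be enrolled. If all were evaluable, the t-test would have 90.7% power, and it stays at or above 80% unless more than 40 of the 150 are lost. That is fair, but the extra patients are there to absorb losses, and section 18 (Resources Available) counts on only 70% of them (105). The ANOVA would have 92.8% at 150, so the t-test still trails.

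Third, the baseline gain rests on an unknown correlation. Percent-predicted scaling for height, sex, ethnicity and age may already remove part of it, and if the 0.40 is the SD of a change or of an adjusted value, the gain is overstated. These limits stand. The scaling does not, however, account for fracture side or for the patient's own function after injury.

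Fourth, section 11 does not rule out a further model or a t-test on change from baseline. Neither is specified. A change score would not be a safe substitute: its SD is 0.40 × √(2(1 − r)) if baseline and follow-up SDs are equal, which exceeds 0.40 whenever r is below 0.5.

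Finally, the figures assume equal numbers of each fracture type. With 40% bilateral, the average effect is 0.6 × 0.30 + 0.4 × 0.15 = 0.24 L and the plain t-test has about 83% power at 104. The ANOVA and the ANCOVA would gain from the same shift, so the ranking does not change.

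**Conclusion.** The concern holds. The planned test is not the one behind the 104, and on the protocol's inputs it has 77.8% power against 81.1%. That part depends only on alpha 0.05 and equal groups. The additional gain from the baseline, up to 84.6–97.8%, depends on an assumed correlation of 0.3 to 0.7 and on reading 0.40 as the within-group SD of a single measurement.

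The reason to act is that better precision costs nothing and the protocol is unsure of its own SD. At the top of its range, 0.60, even the ANOVA has only 47% power at 104; baseline adjustment would raise that to 51%, 59% or 76% at r = 0.3, 0.5 or 0.7. The change should be made, although the trial is not invalid without it.

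**What to change.** In section 11, replace the t-test for spirometry and incentive spirometry with ANCOVA: follow-up value on arm, fracture side and the pre-assignment value of the same measure. If several days are analysed together, use a mixed model with the same terms. In either case:

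- Name the primary measure (FVC or FEV₁) and the primary time point, since the model is undefined without them.
- Make the arm effect pooled over fracture types the primary estimate, state how the two types are weighted in it, and say that the 80% refers to this effect.
- Report unilateral and bilateral results descriptively with confidence intervals, and say that neither they nor the interaction are powered.
- State the alpha level.

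The cost is a wording change, to be made by amendment before the data are examined. Fracture side and both baselines are already collected, and no more patients or visits are needed.

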The study will use a randomized-experimental design and will be randomized via envelope randomization, with experimenters being blinded. A total of 104 patients, 26 in each group, will undergo initial incentive spirometry and force vital capacity (FVC) and FEV₁ tests. Groups will consist of a control versus experimental group, stratified into bilateral and unilateral rib fractures. Three days' worth of data will be collected for each of the tests and will also be collected 24 hours prior to discharge. Length of stays will be compared for experimental and control groups, as well as time to ambulation (collected from the first physical therapy assessment). Injury severity score will also be collected to determine any correlation by severity of injury. Patient satisfaction surveys for the device will also be collected to determine if the patients feel a difference with the device.

4) Background/Scientific Rationale and Significance

Little research as been conducted to determine the significance of a splinting device used in patients with chest trauma, and it is still uncertain whether these devices improve overall patient outcomes. Contradicting studies with similar experimental designs show either some significance (p-value) or insignificance in pulmonary function pre- and post-treatment. This gap in current knowledge leaves room for concern in whether the patient truly benefits from a splinting device in this type of injury. Changes in percent predicted FVC/FEV₁ ratio in this patient population are not readily demonstrated in most of these studies, as well as differing length of stays. This study will contribute to this base of knowledge by determining the effects of the Duracore splinting device on this patient population using the objectives.

5) Inclusion and Exclusion Criteria

Inclusion:

- Adult patient admitted to the trauma service at Penrose Hospital
- Willing and able to comply with all requirements of the study
- Active diagnosis of rib fractures
- Male or female ages 18 and older
- Able to provide written informed consent to participate in the study
- Must be physically able to don and use the splinting device independently without assistance

Exclusion:

- <18 years old
- History of pulmonary disease, lobectomy, or lung transplant
- Current smoker of tobacco products >5 years
- Diagnosis of flail chest

- Pregnant Women
- Prisoners
- Cognitively Impaired; must be alert and oriented x 3

6) Number of Subjects

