Variables to be collected are:

- Age (years)
- Gender
- Diagnosis

CHI Institute for Research and Innovation

- Incentive Spirometry values for this admission
- FVC/FEV1 values for this admission
- Height, Weight, and Ethnicity for FVC/FEV₁ % predicted calculation
- Averages from the patient satisfaction survey using a Likert Scale
- Length of Stays
- Time to Ambulation
- Injury Severity Score

10) Procedures Involved

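### The only between-group test of the lung measures is an unadjusted t-test on an unspecified reading; name one contrast and use the baseline, stratum and repeated readings the trial already collects

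*Combined protocol and SAP*

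**What the plan says.** - Section 11 (Data Analysis Plan) names one between-group test: "Data analysis will include a two-tailed t-test to account for significance between control and experimental groups". It continues: "This will be done with both incentive spirometry and FVC/FEV₁". Otherwise it offers correlations, graphs of trends and survey averages.
- Section 3 gives the schedule: "Three days' worth of data will be collected for each of the tests and will also be collected 24 hours prior to discharge". Section 10 adds that before assignment "baseline values of incentive spirometry (IS) and spirometry will be done", and that further measurement "will occur over three days, and a final collection prior to discharge". The variable list in Section 9 has "Incentive Spirometry values for this admission", with a matching entry for FVC/FEV₁.
- Section 3 stratifies the groups by bilateral and unilateral fracture. Sections 6 and 11 call FVC/FEV₁ the primary variable and size the trial with a 2×2 between-subject ANOVA, which takes one value per patient.
- No section names the time point, change score or per-patient summary to be tested, a model for repeated readings, an alpha level, or an order of testing between the two measures. The primary endpoint in Section 9 is a statement of purpose and does not fill the gap.

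**The concern.** A two-sample t-test needs one independent value per patient. This plan produces up to four post-baseline values per measure: three if the baseline is also the day 1 reading, and perhaps fewer in a short stay. The analyst must therefore choose what to test, and as written that choice can be made after the data are seen. Some choices keep the error rate at 5% and others do not.

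The second problem remains even if the choice is made well. The hypothesis concerns lung capacity over the course of admission, and the trial measures baseline, stratum and several days. A t-test on one reading uses none of that and does not match the model behind the sample size.

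**Working it through.** **Inputs.** From Sections 6 and 11: SD 0.40; control means 1.50 L (unilateral) and 1.35 L (bilateral); splint means 1.80 L and 1.50 L; 26 per cell, 104 in total; 80% power. Assumptions, because the documents give neither: two-sided alpha 0.05, and a correlation ρ of 0.5 to 0.9 between readings.

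**1. The plan's own figure.** Average device effect = (0.30 + 0.15)/2 = 0.225 L. For the main effect in the 2×2 ANOVA, noncentrality = 104 × (0.225/2)² / 0.40² = 8.23 on 1 and 100 df, giving power 0.811. With 25 per cell it is 0.795. So 26 per cell is the smallest size that reaches 80%, and the stated N reproduces.

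**2. The stated t-test on one value per patient, ignoring stratum.** The differences between stratum means enter the SD that the test estimates: √[(0.40² + 0.15² + 0.40² + 0.075²)/2] = 0.417.
- Difference needed for significance: 1.983 × 0.417 × √(2/52) = 0.162 L.
- True standard error with 26 fixed per cell: 0.40 × √(2/52) = 0.0784 L.
- Power ≈ Φ[(0.225 − 0.162)/0.0784] = Φ(0.80) = 0.79. Simulation of 200,000 trials gives 0.787.

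If the numbers per stratum were left to chance, power would be 0.778.

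**3. Error rate by what enters the test.** For k equally correlated tests, P(any |Z| > 1.96) = 1 − ∫φ(u)[Φ((1.96 − √ρ·u)/√(1−ρ)) − Φ((−1.96 − √ρ·u)/√(1−ρ))]^k du. For m readings pooled as if independent, the standard error is too small by a factor √(1 + (m−1)ρ), and the error rate is 2[1 − Φ(1.96/√(1 + (m−1)ρ))].

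| What is tested | ρ = 0.5 | 0.7 | 0.9 |
|---|---|---|---|
| One prespecified value, primary variable | 5% | 5% | 5% |
| Each of 3 times, one measure | 13% | 11% | 8% |
| Each of 4 times, one measure | 16% | 13% | 9% |
| Each of 4 times, two measures | 25% | 19% | 12% |
| 3 readings pooled | 17% | 21% | 24% |
| 4 readings pooled | 22% | 27% | 31% |

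The two-measure row uses one common correlation. With the correlation between measures set at 0.5, simulation gives 27%, 23% and 16%. One value per patient on each of two measures, with either allowed to count, gives about 7% to 10%.

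**4. What the unused data are worth.** Take equal correlation ρ among all readings, baseline included, and express residual variance as a fraction of that of one unadjusted reading.

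| Analysis | Formula | ρ = 0.5 | 0.7 | 0.9 |
|---|---|---|---|---|
| One reading, baseline-adjusted | 1 − ρ² | 75% | 51% | 19% |
| Mean of 2, baseline-adjusted | (1+ρ)/2 − ρ² | 50% | 36% | 14% |
| Mean of 3, baseline-adjusted | (1+2ρ)/3 − ρ² | 42% | 31% | 12% |

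The two-reading row applies if baseline is the day 1 reading.

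**The case against.** The best defence is that the text already points to one value per patient. Section 11 speaks of a t-test in the singular, done for two named measures. The power model has one value per patient. Section 10 treats the pre-discharge reading as the final analysis and omits patients who lack it. The time course is left to graphs. On that reading the primary variable is tested at 5%.

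Much of this stands. A reader might infer that the plan must either run many uncorrected tests or count repeated readings as separate patients, and that its false-positive rate is therefore far above 5%. The documents do not support that. Pooling is stated nowhere, and the plural values in Section 9 belong to a data-collection list. A count of twelve tests would require testing FVC and FEV₁ separately, whereas Section 11 treats FVC/FEV₁ as one item beside IS. The rates above 5% in the working are conditional on choices the plan has not made.

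It is also true that naming one value would make the t-test valid for the primary variable, so this point overlaps with the undefined endpoint. What the defence does not answer is that the plan never adopts the safe reading, leaves IS and FVC/FEV₁ unordered, and drops the stratum and baseline.

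**Conclusion.** The concern holds as a gap in specification plus an inferior choice of method. It does not show that the error rate is inflated. Error control cannot be verified from the text: it is 5% on the primary variable if one value is fixed in advance, and higher under the other routes, by amounts that rest on assumed correlations.

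The power cost of ignoring stratum is small (about 79% against 81% on the plan's own means and SD), but it puts the stated test just below the stated 80%. The larger loss is the unused baseline and repeated readings: with three later readings averaged and baseline adjusted for, about 42%, 31% or 12% of the single-reading variance would remain at ρ = 0.5, 0.7 or 0.9. Turning that into power further assumes that the SD of 0.40 describes a single reading and that the 0.225 L effect is present on every day. The documents support neither assumption.

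**What to change.** Replace the t-test sentence in Section 11 with one linear mixed model per lung measure: patient as the repeated unit, and arm, day, arm-by-day, stratum and baseline as fixed effects. ANCOVA on a per-patient mean, with stratum and baseline as covariates, is a simpler alternative. Then state:

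- **Primary test:** the arm difference in the primary FVC/FEV₁ measure, averaged over the planned post-baseline in-hospital days, at two-sided 5%. Say which days these are and whether baseline counts as day 1.
- **IS:** secondary, tested only if the primary test succeeds.
- **Day-by-day and pre-discharge differences:** confidence intervals only. The pre-discharge reading falls at a different time for each patient, and the device is expected to shorten stay, so it is a poor common time point for the main contrast.

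One primary contrast needs no split of alpha. Bonferroni at N = 104 would lower power on the plan's model to about 72% for 2 tests, 63% for 4 and 53% for 8.

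The cost is analysis-plan wording, slightly more analysis work, and the loss of any claim on IS unless the primary measure succeeds. No new patients or measurements are needed. Make the change before the data are analysed, together with the definition of the primary endpoint and its time point.

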Title: Effects of using the Duracore Splinting Device on Patient Outcomes Related to Chest Trauma

Protocol Version Number: 3

Protocol Version Date: 12/8/2020

CHIRB IRBNet ID: 1517921-3

1) Investigators

Principal Investigator

[name] Title: Registered Respiratory Therapist Department: Respiratory Therapy [contact] Email: [contact]

Co-Investigator:

[name] Title: Registered Respiratory Therapist Department: Respiratory Therapy [contact] Email: [contact]

Co-Investigator:

[name] Title: Registered Respiratory Therapist Department: Respiratory Therapy [contact] Email: [contact]

Co-Investigator:

[name] II, M.D. Title: Surgical Trauma Physician Department: Trauma Services Email: [contact]

2) Funding Source

Financial funding was obtained by grants from local agencies through application processes, along with interviews and assessment of the medical device. The first grant was obtained through the Southern Colorado Society of Respiratory Care in hopes to obtain better choices for treatment for patients with rib fractures. Additional funding was provided by the Penrose Foundation as well.

3) Objectives and Hypothesis(es)

The purpose of this study is to use the Duracore patient operated torso splinting device for patients with chest trauma, including rib fractures, to improve deep breathing and help with reduced hospital length of stays (LOS). The hypothesis of this study is that the use of the Duracore splinting device will reduce hospital length of stays and improve patient lung capacities over the course of admission following chest trauma.

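### The omission rule lets discharge without the final tests remove patients from the length-of-stay comparison, and section 11 does not name that comparison's method

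*Combined protocol and SAP*

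**What the plan says.** **The aim.** Section 3 hypothesises that "the use of the Duracore splinting device will reduce hospital length of stays and improve patient lung capacities over the course of admission", and section 9 repeats it. Section 3 also says "Length of stays will be compared for experimental and control groups, as well as time to ambulation", the latter "collected from the first physical therapy assessment". Sections 6 and 11 make FVC/FEV₁ the primary variable and base the sample size on it. No power claim is made for LOS.

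**Who is analysed.** Section 10 states that "any patients who are discharged without completing the final analysis will be omitted from the study". It also sets out to limit such losses: "Discharge planning will be coordinated with respiratory therapy, so the patient does not go home without completing the survey and final analysis". Section 13 treats the same early discharge as a permissible, not mandatory, ground for withdrawal. It adds deterioration of health as another ground and says data are kept unless the subject specifies otherwise. Section 24, under the heading on cognitively impaired adults, allows omission if cognition is lost after enrolment. No section defines an analysis set.

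**The method.** Section 11 opens with a two-tailed t-test between the groups and continues "This will be done with both incentive spirometry and" FVC/FEV₁. The next sentence reads "Correlations will be made with time to ambulation and length of stays, as well as injury severity score". Section 9 says that a list of outcomes including LOS, time to ambulation "and the injury severity score will be correlated to a control group to determine its' effectiveness".

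**The concern.** A randomised comparison is protected only if whoever was assigned is analysed. Discharge without the final tests, deterioration and loss of cognition can all occur after assignment, and all are plausibly linked to LOS. The first is directly tied to it, because discharge both ends the stay and triggers the omission.

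Final spirometry that was never done cannot be recovered. LOS is different: it is known at discharge for every patient, so the omission discards a usable outcome for no gain on this endpoint. The same holds for time to ambulation wherever the physical therapy assessment is charted.

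At stake is whether an observed LOS difference can be attributed to the splint. Sections 10, 13 and 24 also leave the patient set open, and section 11 leaves the method open, so both could be settled after the data are seen.

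**Working it through.** **1. The plan's own figure.** Sections 6 and 11 give cell means of 1.50 and 1.35 L (control) and 1.80 and 1.50 L (splint), SD 0.40 and 26 per cell. The average splint effect is (0.30 + 0.15)/2 = 0.225 L. The noncentrality of the treatment main effect is 26 × (0.225/0.40)² = 8.23. With F on 1 and 100 df and an assumed two-sided 5% level (none is stated), power is 81.1%; at 25 per cell it is 79.5%. So 104 reproduces, but it concerns FVC/FEV₁ and says nothing about LOS.

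**2. The provisions side by side.**

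| Section | Event | Consequence |
|---|---|---|
| 10 | Discharged without final tests | Omitted, stated as a rule |
| 13 | Same event, or deterioration | Withdrawal permitted; data kept |
| 24 | Cognition lost after enrolment | Omission permitted |

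Keeping data is not the same as analysing them, so section 13 does not cancel section 10. The three provisions give no single answer on whose LOS counts.

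**3. How much it could matter.** The documents give no LOS distribution, so this is an illustration. Assumptions: log-normal LOS, control median 5 days, log SD 0.6, 75 per arm (150 at one to one), pooled t-test on log LOS at two-sided 5%, and omission only among stays under 3 days.

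- Control stays under 3 days: Φ[(ln 3 − ln 5)/0.6] = Φ(−0.85) = 0.197.
- Power with nobody omitted, true splint/control ratio 0.80: |ln 0.80| / (0.6 × √(2/75)) = 0.2231/0.0980 = 2.28, giving 62%.

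Simulation, at least 20,000 trials per setting:

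| Short stays omitted, control / splint | Ratio seen when truth is 1.00 | False positives | Ratio seen when truth is 0.80 | Power at 0.80 |
|---|---|---|---|---|
| 0 / 0 | 1.00 | 5% | 0.80 | 62% |
| 10% / 10% | 1.00 | 5% | 0.80 | 59% |
| 25% / 25% | 1.00 | 5% | 0.81 | 56% |
| 50% / 50% | 1.00 | 5% | 0.83 | 49% |
| 30% / 20% | 0.98 | 5% | – | – |
| 50% / 25% | 0.95 | 8% | – | – |
| 50% / 0 (worst case) | 0.91 | 15–16% | 0.73 | – |
| 0 / 50% (worst case) | 1.10 | 15–16% | 0.91 | 16% |

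The 50%/0 row loses 0.50 × 0.197 × 75 = 7.4 control patients. With control median 4 to 7 days and log SD 0.5 to 0.8, that row's null ratio runs from 0.83 to 0.98 and its false-positive rate from 6% to 28%.

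**4. Direction.** Losing short stays mainly from control favours the splint. Losing long stays mainly from control, as deterioration might do, works the other way: omitting 50% of stays over 10 days from control only gives a null ratio of 1.07, and from the splint arm only 0.94 (about 10% false positives each).

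**The case against.** **A comparison is plainly intended.** Section 3 promises one, section 11 opens with a between-group t-test whose wording is not exclusive, and the section 9 phrase about correlating with a control group may mean correlation with arm, which amounts to a t-test. This stands. A reader might infer that no between-arm LOS analysis is planned; the documents do not support that. What remains is that section 11 ties the t-test to incentive spirometry and FVC/FEV₁ and does not name the method for LOS. That is a secondary point.

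**Omissions may be few.** Section 10 coordinates discharge so that the tests are done, without distinction by arm. This should reduce losses, but the rule still applies to whoever is missed, and no expected number is given. The plan enrols 150 for 104 needed, a margin of 46 (31%). That margin covers withdrawals and incomplete data of every kind. It should not be read as a forecast of early discharges or of imbalance.

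**Bias in favour of the splint is not shown.** Because the splint stays at the hospital (section 23), a reader might infer that staff see splint patients at discharge and miss more controls. The documents do not say who collects the device or when, and controls are due a pre-discharge contact too. That mechanism is conjecture.

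**The large error rates are extremes.** They need 50% omission in one arm and none in the other. With equal or mildly unequal loss the effect is small. This stands.

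**Conclusion.** The point holds in a limited form and is worth fixing. Confidence is high that following section 10 removes patients from the LOS and ambulation comparisons because of an event tied to LOS, and that sections 10, 13 and 24 disagree on the consequence. That section 11 leaves the LOS method unnamed is a lesser drafting gap.

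The size and direction of any bias cannot be known from the documents. On the stated assumptions, equal loss mainly costs power (62% down to 59%–49%) and pulls a true 0.80 slightly towards no effect. Modest imbalance brings false positives to about 5% to 8%, and only one-sided loss of half the short stays brings them to about 15% to 16%. It would be wrong to conclude that the LOS result will be materially biased or will favour the splint. The primary FVC/FEV₁ sample size is not affected by this point.

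**What to change.** In section 11, state for these two outcomes:

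> LOS and time to ambulation will each be compared between splint and control, with an effect estimate and 95% CI, accounting for unilateral/bilateral stratum. All randomised patients are included in their assigned arm using charted values, whether or not the final tests were completed, unless the patient withdraws permission to use the data.

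Then:

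- State that the omission and withdrawal provisions in sections 10, 13 and 24 do not remove patients from these two analyses.
- Reconcile mandatory omission (section 10), permitted withdrawal with data kept (section 13) and permitted omission (section 24).
- Report by arm the number missing the final tests or withdrawn, with reasons.

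Optional details are a log scale for LOS, adjustment for injury severity score, and rules for deaths and for patients who never ambulate.

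The cost is a small amount of chart abstraction for patients who missed the final tests. LOS, time to ambulation and diagnosis are already on the section 9 variable list. No patients, visits or procedures are added.
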